Treatment of Orthostatic Hypotension

NCT00581477

Protocol and Statistical Analysis Plan

November 14, 2003

**CLINICAL RESEARCH CENTER
VANDERBILT UNIVERSITY
PROJECT PROPOSAL #1288**

**Project Title: The Treatment of Orthostatic Hypotension
The Treatment of Orthostatic Hypotension**

Project Number:

IRB Approval Number: 030750

IRB Approval Date: November 14, 2003

Principal Investigator: [name]., Professor of Medicine, Pharmacology and Neurology

Co-Investigator(s): [name]., Division of Clinical Pharmacology
[name], Division of Cardiology
[name], Departments of Medicine and Pharmacology
[name], Division of Clinical Pharmacology
[name], Division of Cardiology
[name], Division of Clinical Pharmacology

HYPOTHESIS

We propose that a systematic trial of medications in patients presenting with a unique and chronic constellation of symptoms of autonomic dysfunction will provide us with information on the pathophysiology of their condition and assist us in optimizing their treatment.

SPECIFIC AIMS

To give a single dose of one or more drugs to determine the effect on orthostatic hypotension in a group of patients with autonomic dysfunction of unknown pathophysiology. Depending on the results of these single-dose trials, we might subsequently do 5-day trials and chronic (approximately 2 months) trials.

BACKGROUND AND SIGNIFICANCE

Norepinephrine (NE) and epinephrine (E) are critical determinants of blood pressure. Moreover, they are also involved in the regulation of autonomic outflow in the brainstem and spinal cord. In the periphery, NE is pressor, but within the central nervous system (CNS) it often depresses sympathetic outflow, resulting in a fall in blood pressure. Thus, any factor that alters the synthesis of these catecholamines can perturb blood pressure at several interacting levels. Tyrosine hydroxylase [(tyrosine to L-dihydroxyphenylalanine (DOPA)] is the rate-limiting step in NE synthesis under almost all circumstances. DOPA decarboxylase converts DOPA to dopamine (DA). Dopamine- β -hydroxylase (DBH) converts DA to NE. Loss of DBH leads to an inability of the neuron to synthesize NE, resulting in a buildup of DA.

In 1986, we, and independently, colleagues in Rotterdam, reported a syndrome in which patients have a congenital absence of the DBH enzyme. Results of a battery of biochemical and physiological tests in DBH-deficient patients helped us to identify the pathophysiology of these patients and enabled us to design an effective treatment.

Occasionally, patients present to the Autonomic Dysfunction Center with a unique constellation of

symptoms of autonomic dysfunction so that they do not fit into a diagnostic category (Orthostatic Intolerance, Pure Autonomic Failure, Multiple System Atrophy, Baroreflex Failure). Some of these patients have severe orthostatic hypotension and resemble those with DBH deficiency, but they do not have the extreme plasma levels of DA. We propose that medication trials in these patients will assist us in optimizing their treatment. Evaluation will be undertaken under controlled conditions with medication and dietary restrictions and will consist primarily of orthostatic blood pressure and heart rate measurements and plasma catecholamine determinations.

Participants will first take part in a study designed to provide information on the pathophysiology of their autonomic problems (The Pathophysiology of Orthostatic Hypotension, IRB#030752, CRC approval pending). Results from this study will help us determine which drug(s) to administer in the proposed protocol.

PRELIMINARY STUDIES

Once the pathophysiology of DBH deficiency was understood, we were able to rapidly develop a specific and effective therapy. Consistent with DOPA and DA reducing blood pressure, the administration of a tyrosine hydroxylase inhibitor, such as metyrosine, raises blood pressure in DBH-deficient individuals. The pressor effect appears to correlate with the metyrosine-associated reduction in plasma DA and DOPA levels and also urinary DA levels. DOPS, or Droxidopa INN:(-)-threo-3-(3, 4-dihydroxyphenyl)-L-serine, is structurally closely related to NE, but has an additional COOH group. It can be pumped up into the noradrenergic nerves and converted into NE by L-aromatic amino-acid decarboxylase without requiring DBH. L-DOPS has been used effectively in the treatment of patients with complete DBH deficiency. It might also improve the blood pressure in patients that have profound orthostatic hypotension but do not appear to have complete DBH deficiency.

EXPERIMENTAL DESIGN AND METHODS

Participants in this study are patients with hypotension, who have undergone evaluation as part of our “The Pathophysiology of Orthostatic Hypotension” protocol (IRB#030752, CRC approval pending). Based on the results of these studies, we will administer medication which we believe might improve their symptoms. We will first test a single dose of one or more drugs with monitoring for 24 hours. A drug or drugs effective at preventing an orthostatic fall in blood pressure might then be tested in a 5-day crossover trial with comparison of effects to placebo. Based on the results of the 5-day trial, a patient might then be given a 2-month trial of the drug, with periodic admissions to the GCRC for assessment of symptoms. The period of time needed to complete this study will depend on the number of medications tested.

Drug withdrawal

Participants must remain off any medications that could affect blood pressure for three days prior to and during study. This includes not only their usual scheduled medications, but also other drugs that might be taken intermittently. If their symptoms are severe enough that they or their physician have concerns that their symptoms may worsen, they may be admitted to the hospital for observation during this portion of the study. While they are an inpatient on the GCRC, their general condition, blood pressure and heart rate will be checked regularly to reduce any risk.

Urine pregnancy test

We will perform a urine pregnancy test every time female participants are admitted to the hospital for this study.

Diet

We will ask study participants to eat a standard diet with no caffeine, 150-mEq/day sodium, 70 mEq potassium, and no substances that interfere with catecholamine synthesis, release or assay for three days prior to and during testing.

24-Hour Urine Collection

Participants will collect their urine for 24 hours every time they are admitted to the hospital for this study. The urine will be analyzed for sodium, potassium, creatinine, and catecholamines.

Orthostatic vital signs

Orthostatic vital signs will be measured several times a day. This testing consists of blood pressure and heart rate measured while patients are lying down and then repeated after standing quietly for 5 minutes, using the Dinamap.

Single-dose drug trials

Participants will be admitted to the Vanderbilt Clinical Research Center the evening prior to the study. In the morning, the patients will be seated or in bed for a 30 min baseline period of blood pressure and heart rate monitoring. The medication will be given by mouth, and blood pressure and heart rate will be monitored every 10-15 minutes for the first hour, using a Dinamap. Orthostatic vital signs will be taken after 1, 2, 3, 4, 8, and 12 hours. Fifteen ml of blood will be collected through a saline lock during baseline and after 2, 4, and 8 hours while in the supine and standing positions to measure catecholamines (total of 4 samples lying down and 4 samples upright). Aldosterone will also be measured in blood collected during baseline and at one other timepoint, depending on the duration of the drug effect (total of 2 samples lying down and 2 samples upright). A second blood sample will be collected with the aldosterone and an aliquot of plasma frozen for possible analysis of plasma renin activity. Urine will be collected from 0-7 hours, 7-12 hours and 12-24 hours for measurement of catecholamines. Depending on how well the drug is tolerated and the degree of improvement in orthostatic vital signs and symptoms following the drug, another single-dose drug trial might be scheduled 48 hours after the first or the patient might be asked to start a 5-day trial of the drug at that time. If they are not scheduled for another trial at this time, they can be discharged. The medications include domperidone, metyrosine, L-DOPS, alpha-methyldopa, L-dopa, carbidopa, atomoxetine, and placebo.

Single-dose trial

Time	Days 3,2 pre-study	Day 1 pre-study	Study Day							
			0 hr	1 hr	2 hr	3 hr	4 hr	8 hr	12 hr	24 hr
Drug/diet restriction	X	X	X	X	X	X	X	X	X	X
Urine collection		X	X	X	X	X	X	X	X	X
Admission to GCRC		X								
Pregnancy test		X								
Drug administration			X							
Blood sample			X				X	X	X	
Vital signs		X	X	X	X	X	X	X	X	

5-Day drug trials

Once the appropriate dose has been decided, we will conduct a single-blinded crossover trial. Depending on where they live and the severity of their symptoms, participants might be able to go home

for part of this study. However, after 4 days on the drug (or placebo), they will be admitted to the GCRC. They will be supine and NPO after midnight. In the morning, we will do a Posture Study to determine the effectiveness of the treatment. Before breakfast, we will draw 15 ml of blood while they are supine and another 15 ml after they have stood for 30 minutes to measure catecholamines and aldosterone. A second blood sample will be collected with the aldosterone and an aliquot of plasma frozen for possible analysis of plasma renin activity. We will monitor blood pressure and heart rate during this study, using a Dinamap. Standing time will be determined, and the participants will be asked about their symptoms periodically during the study. For at least three days following this testing, participants will take no medication. They will then start a 5-day regimen of the medication, if they previously took the placebo, or placebo, if they previously took the medication. They will not be told whether they are taking active drug or placebo. The Posture Study will be repeated in the GCRC after the second 5-day period.

5-day trial

Time	Day 3 pre-study	Days 1,2 pre-study	Study day 0	Study days 1,2,3		Study day 4	Study day 5	Study days 6,7		Study day 8	Study days 9,10,11			Study day 12	Study day 13
Drug/diet restriction	X	X	X	X	X	X	X	X	X	X	X	X	X	X	X
Urine collection						X								X	
Admission to GCRC						X								X	
Pregnancy test	X														
Drug/placebo administration			X	X	X	X				X	X	X	X	X	
Posture study/Blood sample							X								X
Vital signs						X	X							X	X

Depending on the results of the 5-day trial, participants will be given a longterm trial of a drug. At the initiation of treatment, and after two weeks, four weeks, and eight weeks of drug, they will be evaluated by a posture study, 24-hour urine collection and assessment of their symptoms. The dose of the medication will be adjusted after two and four weeks of treatment if there has been insufficient improvement in blood pressure (able to stand with < 20 mmHg decrease in systolic blood pressure) or symptoms.

Chronic trial

Days	-3,-2	-1	0	1-10	11,12	13	14	15-24	25,26	27	28	29-52	53,54	55	56
Restrict diet	X	X	X		X	X			X	X	X		X	X	X
Collect urine		X				X				X				X	
Admit to GCRC		X				X				X				X	
Pregnancy test		X				X				X				X	
Take Drug			X	X	X	X	X	X	X	X	X	X	X	X	
Posture study/ Collect blood			X				X				X				X
Vital signs		X	X			X	X			X	X		X	X	X
Adjust dosage							X				X				

BIOSTATISTICS

Statistical analyses will be performed on a personal computer with the statistical package SPSS for Windows (Version 10.0, SPSS, Chicago). Some paired comparisons (Paired t-test, Wilcoxon signed-rank test, repeated measures ANOVA, Friedman ANOVA by ranks) might be needed to compare treatment responses within a subject.

Protection of Human Subjects:

POPULATION:

The conduct of these studies will involve approximately 25 human subjects. Subjects will include patients with severe orthostatic hypotension and other autonomic symptoms who do not meet criteria for one of our standard diagnoses. Potential study participants will first take part in "The Pathophysiology of Orthostatic Hypotension" (IRB #030752, CRC approval pending). Results from that study will provide information on the pathophysiology of the autonomic disorder and might suggest which medication(s) might be an effective treatment. Subjects will range in age from 18-70 and be non-smokers, drug-free, able to give informed consent, and free of pulmonary, renal, hematopoietic, hepatic and cardiac disease. Exclusion criteria for the study include smoking, pregnancy, medications affecting the autonomic nervous system, any chronic illness, and anemia (Hct<35).

RESEARCH MATERIALS:

Research materials include blood, urine, and data. The blood will be analyzed for catecholamines, renin and aldosterone. Urine will be analyzed for catecholamines, sodium, potassium, and creatinine.

RECRUITMENT OF SUBJECTS:

We will recruit patients from those referred to the physicians of the Autonomic Dysfunction Center at Vanderbilt who have participated in "The Pathophysiology of Orthostatic Hypotension" (IRB #030752, CRC approval pending). In each instance, the investigator will describe the complete protocol to the prospective participant. The subjects will then be given a written informed consent form that has been approved by the Vanderbilt Institutional Review Board. The subject will be given adequate time to read the consent form, ask questions, and if satisfied by the responses, sign the form. Consent or refusal to participate in this study will not affect medical care. No modifications or waiver of the elements of consent have been authorized, nor will any be necessary in the execution of this study.

POTENTIAL RISKS:

Blood drawing and insertion of venous catheters are uncomfortable and may cause bruising, bleeding, permanent damage to the vessel and in rare instance, infection. The risk of bleeding can be prevented by tight compression of the site. Experienced personnel will place all intravascular lines using sterile technique.

Consuming a sodium- and caffeine-controlled diet might not be to the subject's taste preferences. If a subject drinks caffeinated beverages regularly and stops caffeine intake suddenly, he/she might have headaches and fatigue for a few days. These symptoms can be avoided by cutting down gradually on the amount of caffeine in the diet.

Stopping medications might cause a temporary worsening of symptoms for patients. Careful monitoring of blood pressure and heart rate will permit immediate attention and termination of the protocol when necessary.

Collection of urine can be inconvenient.

The seated oral medical trials are tedious and boring because they require being seated for an extended period of time while blood pressure is monitored.

When any medication is used in testing, there is a small risk of an unforeseeable life-threatening allergic reaction. Side effects associated with specific medications are listed below. Side effects are listed as common, uncommon, and rare.

Domperidone – common: dry mouth, abdominal cramps, diarrhea. Uncommon: loss of balance or muscle control, swelling of mouth, increased breast milk flow, headache, hives, hot flashes. Rare: pounding or racing heart beat, swelling of extremities, change in appetite, constipation, dizziness.

α -Methyldopa – common: weakness, distention of lower abdomen, constipation, swelling of the lower extremities, fever and depression, anxiety, nightmares, being sleepy or drowsy, headache and dry mouth. Uncommon: dizziness, gas, diarrhea, chest pain, stuffiness of the nose, low blood pressure on standing, low heart rate, nausea or vomiting, abnormal liver function tests. Serious or life-threatening: extremely rare reactions are fatal liver damage and fatal inflammation to the heart.

Carbidopa – only reported to have adverse effects when it is given with the drug levodopa for Parkinson's disease. Common adverse events with the carbidopa-levodopa combination include dyskinesias and nausea. Less common adverse effects are psychotic episodes, depression and dementia.

Metyrosine – common: drowsiness, diarrhea, drooling, trembling and shaking of hands and fingers; trouble speaking. Uncommon: decreased sexual ability in men, dry mouth, nausea, vomiting, stuffy nose, anxiety, confusion, hallucinations, mental depression. Rare or life-threatening: crystalluria (the excretion of crystals in the urine resulting in urine retention), black, tarry stools, unusual bleeding or bruising, muscle spasms, painful urination, pinpoint red spots on skin, restlessness, shortness of breath, shuffling walk, skin rash and itching, swelling of feet or lower legs, tic-like movements

L-Dopa (levodopa) – common: abdominal pain, dry mouth, loss of appetite, nightmares, gas, abnormal thoughts, agitation, anxiety, clumsiness, difficulty swallowing, dizziness, excessive watering of mouth, nausea and vomiting, uncontrolled body movements. Uncommon: Chest pain, mood or mental changes, discoloration of sweat or urine, constipation, diarrhea, flushed skin, headache, hiccups, increased sweating, muscle twitching, trouble sleeping, blurred vision, difficult urination, dilated pupils, dizziness or lightheadedness when getting up from a lying or sitting position, double vision, fast or pounding heartbeat, hot flushes, mental depression, skin rash, weight gain or loss. Rare: back or leg pain, black tarry stools, chills, convulsions, fever, high blood pressure, loss of appetite, swelling of feet or lower legs

Atomoxetine – common: headache, nausea, sleepiness, trouble sleeping, anxiety, dry mouth, loss of appetite, dizziness, constipation, flushed or warm sensation, rash. Uncommon: loose stools, excessive energy, excitement, stomachache ache, fluttering sensation in chest, abnormal heart rhythm sensations, tingling, vomiting, aching muscles. Rare: abnormal blood tests, such as abnormal liver function tests

L-DOPS – The use of L-DOPS is under investigation and is not approved by the FDA. We have used it for many years in a small population of patients that lack dopamine-beta-hydroxylase, the

enzyme that converts dopamine to norepinephrine. The initial dose is low and adjusted to treat low blood pressure without adverse effects. It is possible that there may be some side effects. The following rare side effects have been reported: increased blood pressure, nausea, headache, hallucination, anorexia, increased liver enzymes, dizziness/lightheadedness, heart fluttering, thirst, nervousness, stomachache, vomiting, abdominal pain, chest pain, and fatigue.

Placebo – The placebo is a pill or capsule that does not contain active ingredient. It should therefore have no side effects.

PROTECTION:

Monitoring of vital signs will help minimize potential risks. All information will be kept strictly confidential.

BENEFITS:

We guarantee no direct benefits to the study participants. Results of this study will improve our understanding of autonomic dysfunction and might lead to important advances in the management of these diseases.

DATA SAFETY MONITORING PLAN

Data from subjects enrolled in this study will be reviewed on a bi-monthly basis by the P.I. and at least one co-investigator. Any adverse event of a serious or greater nature will be reviewed immediately with the P.I. [name]. will be responsible for tracking adverse events in this study.

The adverse event will be described with the following information: description of the event; outcome of the event; duration of the event; relationship to study procedure; requirement, if any, for treatment or intervention; and outcome.

Adverse events will be graded according to the following scale:

0 = No adverse event or within normal limits

1 = Mild adverse event (transient and mild in nature, and no treatment is necessary)

2 = Moderate adverse event (some intervention and treatment are necessary, but participant completely recovers)

3 = Severe adverse event (an event that results in hospitalization, disability, or death or is life-threatening)

The investigator will state his opinion on whether there is a reasonable possibility that the event or experience is related to a procedure performed as part of this study.

JUSTIFICATION FOR GCRC UTILIZATION

The following GCRC services are necessary for conducting this scientific study:

Inpatient/Outpatient Support: Approximately 25 patients will be studied over the five years. The length of stay and number of admissions will depend on the number of medication trials performed with each patient. A research nurse will be needed to draw blood and monitor blood pressure during pharmacological testing, to document pulse and blood pressure during orthostatic vital signs, to perform posture studies, and to assist with urine collections, as well as for general patient care.

Biostatistical Support: Although we do not anticipate doing any data analysis, review by the GCRC biostatistician is requested, as well as assistance with any unforeseen data analysis.

Informatics Support: Review by the Informatics specialist and access to data from the Core Lab is required.

Core Lab Utilization: The Core Lab is needed for plasma and urine catecholamine analysis and urinary sodium, potassium and creatinine.

Nursing Support: Nursing support will be needed for blood draws, urine collections, posture studies, and medication studies.

Nutrition Services Utilization: We will ask patients to eat a standard diet with no caffeine and 150 mEq sodium, 70 mEq potassium while in the hospital for these procedures. We might ask them to restrict their diet for up to three days prior to admission.

OTHER SUPPORT

84 urine pregnancy tests are needed.

700 plasma aldosterone and 50 plasma renin analyses are requested, as well as processing of 650 aliquots of plasma to be frozen for possible future analysis of plasma renin activity.

Gender/Minority Mix

This study does not exclude research participants by race or gender and includes research participants aged 18 – 70 years old. We expect the overall distribution of participants to be even across gender and ethnic groups.

Table I – National Figures for Mix of Study Population

	Am. Indian Alaskan Native	Asian Pacific Islander	Black, of Origin	Hispanic	White, of Origin	Other	Total
Male	0.4	1.4	5.7	4.3	36.9	*	48.7
Female	0.4	1.4	6.0	4.5	38.8	*	51.1
Total	0.8	2.8	11.7	8.8	75.7	*	99.8

* negligible in this context. Note: Rounding errors led to totals different from 100%.

Table II – Tennessee Figures for Mix of Study Population

	Am. Indian Alaskan Native	Asian Pacific Islander	Black, of Origin	Hispanic	White, of Origin	Other	Total
Male	0.1	0.5	7.4	0.4	39.9	*	48.3
Female	0.1	0.5	8.0	0.4	42.8	*	51.8
Total	0.2	1.0	15.4	0.8	82.7	*	100.1

* negligible in this context. Note: Rounding errors led to totals different from 100%.

Table III – Anticipated Enrollment – Actual Patient Numbers

	Am. Indian Alaskan Native	Asian Pacific Islander	Black, of Origin	Hispanic	White, of Origin	Other	Total
Male	0	0	2	1	10	0	13
Female	0	0	2	0	10	0	12
Total	0	0	4	1	20	0	25

REFERENCES

Man in 't Veld AJ, Boomsma F, Lenders J, Meiracker Avd, Julien C, Tulen J *et al.* Patients with congenital dopamine b-hydroxylase deficiency. A lesson in catecholamine physiology. Am J Hypertens 1988;1:231-38.

Man in 't Veld AJ, Boomsma F, Moleman P, Schalekamp MA. Congenital dopamine-b-hydroxylase deficiency: A novel orthostatic syndrome. Lancet 1987;1:183-87.

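### Single-dose days draw at least 120 ml of blood each and can repeat at 48 hours with no repeat Hct, so a patient entering just above 35 could fall below that entry mark without any planned test showing it

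*Combined protocol and SAP*

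**What the plan says.** The Single-dose drug trials section of the protocol states that "Fifteen ml of blood will be collected through a saline lock during baseline and after 2, 4, and 8 hours", in both postures, and gives the total as four lying and four upright samples. Aldosterone is taken at two of the time points, two lying and two upright, and "A second blood sample will be collected with the aldosterone"; the volume of that second sample is not given.

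The same section sets out what may come next. If tolerability and response allow, "another single-dose drug trial might be scheduled 48 hours after the first or the patient might be asked to start a 5-day trial". A patient with no further trial scheduled can be discharged. The list of medications has seven drugs and placebo. Experimental Design and Methods adds that "The period of time needed to complete this study will depend on the number of medications tested". No maximum number of single-dose days appears in the text available.

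Hct appears once, under Population, where anemia (Hct below 35) is an exclusion. Research Materials lists catecholamines, renin and aldosterone as the blood analyses. The schedule tables show no blood count, and the Protection paragraph relies on vital signs.

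**The concern.** The protocol uses Hct 35 as its own line for who is too anemic to enter, and then takes a material amount of blood, possibly several times within a week, without measuring Hct again. A patient admitted just above the line could be moved below it by the sampling alone and still be dosed and bled again.

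These patients have severe orthostatic hypotension and must stand repeatedly. Their usual treatment is also withheld: "Participants must remain off any medications that could affect blood pressure for three days prior to and during study". Standing pressure is therefore expected to be low whatever the red-cell mass, and vital signs cannot single out blood loss as a cause. What is at stake is a modest safety margin for individual patients.

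**Working it through.** **Inputs from the protocol.** 15 ml per sample, four time points and two postures (Single-dose drug trials); 48-hour repeat (same section); Hct limit 35 (Population); 700 aldosterone assays and 84 pregnancy tests (Other Support); 25 patients, of whom 12 are expected to be women (Table III).

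**Inputs assumed.** Blood volume V of 4 to 6 L, full plasma refill between days and, in the main case, no red-cell regrowth. None of these is in the documents.

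**1. Blood per day.** 4 time points x 2 postures = 8 samples, which reproduces the stated 4 + 4. Then 8 x 15 = 120 ml. Reading 15 ml as a per-posture amount is supported by the 5-Day drug trials section: "we will draw 15 ml of blood while they are supine and another 15 ml after they have stood for 30 minutes". The four second samples come on top, so 120 ml is a floor.

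**2. Blood drawn on earlier drug days.** 120 ml before drug 2, 240 ml before drug 3 and 360 ml before drug 4.

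**3. Entry Hct that falls to 35.** After n drug days, Hct = entry Hct x (1 - 120/V)^n, so the threshold at entry is 35/(1 - 120/V)^n.

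| V | before drug 2 | before drug 3 | before drug 4 |
|---|---|---|---|
| 4 L | 35/0.970 = 36.1 | 35/0.941 = 37.2 | 35/0.913 = 38.3 |
| 5 L | 35/0.976 = 35.9 | 35/0.953 = 36.7 | 35/0.930 = 37.6 |
| 6 L | 35/0.980 = 35.7 | 35/0.960 = 36.4 | 35/0.941 = 37.2 |

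Example at 5 L: entry at 36 gives 35.1, 34.3 and 33.5 before drugs 2, 3 and 4.

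**4. Sensitivity before drug 4.**
- Regrowth of r ml of red cells per day, over two days between doses. Work back from 0.35 x 5,000 = 1,750 ml of red cells by applying (m - 2r)/0.976 three times. For r = 5: 1,782.8, 1,816.4, 1,850.8 ml, an entry Hct of 37.0. For r = 10: 1,772.5, 1,795.6, 1,819.3 ml, an entry Hct of 36.4. At r = 20 the edge is 35.1, so fast regrowth nearly closes the band.
- If 15 ml covered both postures (60 ml per day, the less natural reading), the 5 L edge is 36.3.
- If the second samples were 5 or 10 ml each (120 + 20 = 140 or 120 + 40 = 160 ml per day), the 5 L edge is 38.1 or 38.6.
- Entry at 40 stays above 35 within the 4 to 6 L range. The worst case is 4 L at 160 ml per day: 40 x 0.885 = 35.4.

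**5. Is a series of four days plausible?** Aldosterone: 700/25 = 28 assays per patient. A single-dose day uses 4, a crossover 4 (two posture studies at 2 each) and a chronic trial 8 (four posture studies at 2 each). So 28 = 4k + 4m + 8c, for k single-dose days, m crossovers and c chronic trials. A crossover drug must first have worked as a single dose ("A drug or drugs effective at preventing an orthostatic fall in blood pressure might then be tested in a 5-day crossover trial"), and a chronic trial follows a crossover, so c ≤ m ≤ k. The solutions with c = 1 are (k, m) = (4, 1) and (3, 2); with c = 0, k runs from 4 to 7. A typical budgeted patient therefore has at least three single-dose days.

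Pregnancy tests: 84/12 = 7 per woman. With one test per admission, (4, 1) with one chronic trial leaves 7 - 2 - 4 = 1 single-dose admission, that is, four drug days in one stay. With only the one test per crossover shown in the 5-day table, (4, 1) leaves 7 - 1 - 4 = 2 admissions, and (3, 2) leaves 7 - 2 - 4 = 1. The budgets suggest three or four days. They are averages and do not fix the sequence.

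**The case against.** Hct 35 is an entry criterion. Nothing in the protocol makes it a limit for continued dosing, and a reader who inferred that dosing below 35 breaches the protocol would be going beyond the text. That objection stands; the point is only that the study can move a patient across its own line without a measurement that would show it.

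The size of the band depends on assumptions. Quoting 37.6 alone would hide a 5 L blood volume, no regrowth and four consecutive days at 48-hour spacing. The one repeat that the protocol spells out puts at risk only patients entering within about one point of 35, and drugs are chosen from the preceding pathophysiology study, so nobody is expected to run through the whole list. This also stands, and is why ranges are given.

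There are clinical safeguards: orthostatic vital signs at 1, 2, 3, 4, 8 and 12 hours, regular checks of general condition, a next step that depends on tolerability, termination when necessary, and adverse-event review. They watch for the consequence that matters most, poorer standing tolerance, but they do not measure red-cell loss. The consent pages and the preceding pathophysiology protocol were not available, and either could contain a blood limit or a further count.

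A reader might also infer that later drugs in a series would look worse because the patient has been bled. The documents give no basis for an effect on the drug comparisons, and none is claimed.

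**Conclusion.** Cheap improvement (minor patient safety). At least 120 ml per drug day, a possible repeat at 48 hours, no stated cap and no Hct after entry all follow from the text. With 4 to 6 L blood volume, full refill and no regrowth, the exposed entry range is 35 to about 36 before drug 2. If four days run back to back, its upper edge before drug 4 lies between about 37.2 and 38.3, and it is lower with regrowth.

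It would be tempting to conclude that the design makes patients anemic or harms them. The documents do not support that: they give no entry Hct values, so the number affected is unknown and may be zero, and nothing shows that an Hct just under 35 causes harm.

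**What to change.** Before each further single-dose day, read an Hct on a small part of the supine baseline sample already drawn before the dose. Read one also before a 5-day trial that starts directly after the series. That trial's table shows no blood draw at its start, so this reading needs a small extra sample.

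If the value is 35 or more, go on as planned. If it is below 35, hold the dose and further sampling until the investigator decides whether to postpone the remaining single-dose days or to continue, and records the reason. Automatic discharge and readmission is not needed: it would mean a second three-day medication withdrawal, and Potential Risks acknowledges that stopping medication may temporarily worsen symptoms.

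Cost: one inexpensive test per repeat day, 25 x 3 = 75 if every patient has four days or 25 x 2 = 50 if three, plus at most 25 more if every patient goes straight into one 5-day trial. Some series may be delayed or split. A split series would bring a second withdrawal and diet restriction and, for a woman, one more pregnancy test.
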